6.8. Unscheduled Visit

An extra visit can be performed at any time when there is a need for it, as judged by the Investigator. In case of values outside the normal range, the DSMB can request an extra visit where additional examinations should be conducted and blood sample(s) drawn as agreed with the DSMB.

7. STUDY PROCEDURES

The schedule of activities is provided in [Table 1](#). Study assessments will be performed by the investigator, delegated study personnel or central reader. Patient related events and activities, including specific instructions, procedures, concomitant medications, administration of the study drug; steroid tapering and descriptions of AEs should be recorded in eCRF.

7.1. Central reading

During the endoscopy a video will be recorded (separate instruction will be provided). These videos will be sent to trained central readers for assessment.

7.2. Concomitant Medication

All changes to the prior treatment need to be recorded during the study e. g. stop date or entry of a new treatment.

7.3. Collection of Adverse Event and Serious Adverse Event

Collection of AE will start directly after an Informed Consent is signed. During the screening period only AEs related to study procedure will be reported. Definitions, documentation and reporting of AEs are described in detail in Section 8.

7.4. Demographics

Patient demographics, including sex, age, and race will be collected at the screening visit 1a.

7.5. Electrocardiogram

A 12-lead ECG will be performed and assessed at visit 1a, 2b and 6. At visit 2b the ECG should be taken before study drug administration (after 5 minutes rest) and another ECG approximately 30 minutes after study drug administration. The ECG will be reviewed by the investigator. If abnormalities before first dose of study drug the findings should be reported as medical history. Findings during study should be reported as AEs.

7.6. Eligibility and Evaluation

At visit 1a, the investigator should estimate the patient's eligibility to the study based on Medical History, UC History and Concomitant therapy. Patient should also be asked about number of daily stool and presence of rectal bleeding. The combined information gives information to decide if patient is eligible for endoscopy.

For assessing eligibility to the study (Mayo score of 6-12) the Modified Mayo score at visit 2a, will be calculated by summarising the visit 1b endoscopy sub score, the PGA assessment and the Mayo sub scores assessed from eDiary at visit 2a.

All components for the assessment of Mayo score have to be collected within 10 days before visit 2b.

7.7. Endoscopy, Biopsy and Histology

A full colonoscopy will be performed with a video endoscope, at the Screening Visit (1b). The endoscope should inspect the whole bowel, up to the Cecum. Three biopsies should be taken from each bowel segment investigated (ascending colon, transverse colon, descending colon, sigmoid colon, and rectum). These biopsies will be used for central read histopathological evaluation (in end of the study) ([appendix 15.3](#)) and future biomedical research (if consented to, if not consented only two biopsies from each segment will be taken). There is a centralised assessment and processing of the endoscope videos.

A flexible sigmoidoscopy, performed with a video endoscope will be performed at visit 6. The endoscope should inspect the left-sided colon, up to splenic flexure. Three biopsies should be taken from each bowel segment investigated (descending colon, sigmoid colon, and rectum). The biopsies will be used for central read histopathological evaluation (in end of the study) and future biomedical research (if consented to, if not consented only two biopsies from each segment will be taken). There will be a centralized assessment and processing of the endoscope videos.

Separate instructions for procedure preparations will be provided to the patients.

7.8. Extraintestinal Manifestation Assessment

Patient will be asked questions ([appendix 15.4](#)) about specific diseases at visit 2b, visit 6 and visit 7. [\[20\]](#)

7.9. Inflammatory Bowel Disease Questionnaire

IBDQ is a patient questionnaire with 32 questions grouped into four dimensions: bowel, systemic, social, and emotional. The IBDQ will be completed at visit 2b before study drug administration, visit 5 and visit 6 or early termination visit.

7.10. Informed Consent

All patients will receive written and verbal information concerning the study prior to any study related procedures. The given information emphasises that participation in the study will be voluntary and that the patient might discontinue and/or withdraw consent from the study at any time and for any reason. All patients will be given the opportunity to ask questions about the study and will be given sufficient time to decide whether to participate in the study or not. Patient's consent will be sought regarding data that will be recorded, collected, processed and might be transferred to the European Union (EU) and non-EU

countries. The data will not identify any person taking part in the study, in accordance with the EU Data Protection Directive (95/46/EU).

A copy of the patient information, including the signed ICF, will be given to the patient.

7.11. Laboratory Procedures

Blood, urine and stool samples will be collected at the time point identified in schedule of activities ([Table 1](#)). All samples will be collected in a non-fasting state. The clinical analyses to be performed are listed in [Table 3](#). Unscheduled clinical labs may be obtained at any time during the study to assess any perceived safety concerns.

All females will have a serum pregnancy test at visit 1a and urine dip stick test at visit 2b, 3, 4, 5 and 6; it should be completed prior to each dosing of study drug.

A central laboratory will be used to perform safety tests for haematology and blood chemistry. Central laboratory will also analyse urine (microscopy and/or culture) if the urine dipstick analysis are clinically significant. Safety laboratory reports will show the reference range for each variable and will be reviewed at each visit. In the event of an unexplained clinically noteworthy abnormal laboratory test value, the test should be immediately repeated and followed-up until it has returned to the normal range and/or an adequate explanation of the abnormality is found. Clinically significant abnormal findings should be recorded as AEs.

For the purpose of Future Biomedical Research (if consented to), serum and biopsy specimen's may be collected (if not consented no extra samples will be collected) during this clinical trial. The collected specimens may be used for future assay development and to explore and identify biomarkers that enhance the scientific understanding of ulcerative colitis and/or the therapeutic treatment. Such research is for mode of action biomarker testing to address emergent questions not described elsewhere in the protocol (as part of the main trial) or development of UC evaluation score and will only be conducted on specimens from appropriately consented subjects.

The signed and interpreted laboratory results will be kept together with the patient's source data as supplemental pages.

Table 3. Clinical Laboratory Analysis.

Haematology	Clinical Chemistry	Urine	Other
Hemoglobin ¹	Albumin ¹	Blood ²	Faecal Calprotectin ⁴
Hematocrit ¹	ALP ¹	Glucose ²	Stool culture for;
Platelet count ¹	ALT ¹	Ketones ²	
 • Clostridium DifficileToxin B
RBC s ¹	AST ¹	Leucocytes ²	
 • Shigella
WBCs ¹	Amylase ¹	Nitrite ²	
 • Campylobacter
Platelets ¹	BUN ¹	Protein ²	
 • Yersinia
Neutrophils ¹	Calcium ¹	pH ²	
 • Salmonella
Eosinophils ¹	Chloride ¹		
 • Faecal Ova and Parasites
Monocytes ¹	CPK ¹		Urine pregnancy test ³
Basophils ¹	Creatinin ¹		Pregnancy test ³
Lymphocytes ¹	CRP ^{1,4}		Triglycerides ¹
	GGT ¹		Cholesterol ¹
	Glucose ¹		Fibrinogen ¹
	Phosphorus ¹		APTT ¹
	Potassium ¹		PT (including INR) ¹

	Sodium ¹ Total Bilirubin ¹ Total Protein ¹ Uric Acid ¹		Future Biomedical Research ¹ Colon biopsies ⁵
--	---	--	--

¹ non-fasting state

² dip stick in all cases; microscopy and or/culture if clinically indicated.

³ for women of childbearing potential

⁴ for biomarker assessment

⁵ Central read histopathological evaluation.

7.12. Leakage Measure

Weigh the under pad/surface protection sheet before the patient gets on the bed. After the drug has been administered and patient has been lying for 30 minutes weigh the under pad/surface protection again. The outcome will be registered in the eCRF.

7.13. Medical History

A complete medical history will be collected covering information up to the first dose of study drug. Diagnosis/symptoms/signs and the start year will be collected. Findings and/or abnormalities detected by physical exam and ECG interpretation at Visit 1a should be reported on medical history, preferably as a diagnosis. Information regarding postmenopausal status will be collected as medical history.

7.14. Mayo Score

- Full Mayo Score

A full Mayo score includes the sub scores; stool frequency, rectal bleeding, endoscopy and PGA.

- Modified Mayo Score

The Modified Mayo Score excludes the friability at grade 1 for the endoscopic sub score.

The Modified Mayo Score excluding friability at grade 1 ([appendix 15.1](#)), [21] will be used at visit 2b, to evaluate eligibility to the study.

The sub scores stool frequency and blood in stool will be evaluated during screening period, using eDiary data for the sub scores. The endoscopy sub score will be assessed by using centrally read result from a full colonoscopy (performed within 10 days prior Visit 2b) or sigmoidoscopy (at Visit 6).

- Patient Reported Outcome

PRO2 includes the sub score; stool frequency and rectal bleeding reported daily by the patient and via an eDiary.

7.15. Patient eDiary completion and Review

A Patient eDiary will be used for data collection with regard to patients daily symptoms. The following symptoms will be assessed daily from visit 1a to visit 7.

- Absolute number of stools

- Stool frequency according to the Mayo sub score
- Blood in stool scoring according to the Mayo sub score

eDiary data will be used to calculate the sub scores stool frequency and rectal bleeding (PRO2).

7.16. Physical Examination

A complete physical examination should be performed at each visit and should include the following body system evaluations: general appearance, skin, musculoskeletal, eyes, ears, nose, throat, thyroid, cardiovascular, chest, abdomen, lymph nodes and neurological examination. If clinical significant abnormalities, it should be reported either as medical history (during screening) or as an AE (after first dose).

7.17. Pregnancy Test

Pregnancy tests will be performed on all females of childbearing potential at all visits up to Week 6. Serum pregnancy tests will be carried out at Visit 1a. Pregnancy tests done at Visit 2b, 3, 4, 5 and 6 will be performed with urine dipsticks. If the pregnancy test is positive this is considered as an AE, contact the CRA for further guidance.

7.18. Prior Therapies

The use of any concomitant therapy will be recorded with preferably generic name and start and stop date. For all non-UC therapy the last 8 weeks treatment prior to Screening visit 1a needs to be recorded. For UC treatment such as: GCS, MMX Budesonide, 5-ASA/SP, AZA/6-MP, TNF- α inhibitor, anti-integrins, cyclosporine, tacrolimus or other immunomodulatory/immunosuppressant drugs, generic name, start date and stop date (if applicable) and dose should be recorded unless when treated. Only need to record the last treatment period for each. The reason why these drugs were not restarted when patient relapsed has also to be reported.

7.19. Study Drug Administration

Study drug will be administered via a rectal enema (see separate instructions).

7.20. Tobacco Use

The patient's tobacco history/use will be collected at Visit 1a and Visit 6.

7.21. Ulcerative Colitis History and Assessment

A detailed history of UC, including month and year of diagnosis, and disease severity will be collected. Information of what is the patients normal stool frequency when in remission duration of flare and number of flares per year will also be collected, as well as the patient's stool frequency prior to the initial onset of signs and symptoms of UC.

Definition of stool

Patients should be instructed that a stool is defined as a trip to the toilet when the patient has either a bowel movement, or passes blood alone, blood and mucus, or mucus only.

Definition of remission reference stool frequency

The patient should be asked to identify at the visit 1a how many stools he or she had in a 24-hour period when in remission from UC.

If the patient does not report that he or she has achieved remission, then the patient should be asked to identify the number of stools he or she had per day before initial onset of signs and symptoms of UC.

7.22. Urgency of Defecation

Patient will be asked questions ([appendix 15.5](#)) [22] about defecation urgency at visit 2b, 3, 4, 5, 6 and 7.

7.23. Vital Signs

Systolic and diastolic BP (mmHg) and HR (beats/min) will be measured in sitting position and after 5 minutes rest at every visit. The use of automated devices for measuring BP and HR are acceptable. Blood pressure and HR should be measured before blood samples are taken. On dosing days, vital signs should be obtained prior to treatment. Body temperature (°C) will be measured and weight and height will be measured or reported from patient at visit 2b.

8. Adverse Event

Collection of AEs will start directly after the ICF has been signed. During the screening period only AEs related to study procedure will be reported.

Investigators are responsible for recording all AEs observed during the study period (i.e., from the time patient signs the ICF and until the patient has completed the study, (only AEs related to study specific procedures at screening visit will be recorded at Visit 1 and 2 while any other medical finding will be recorded as medical history). Following study drug administration, the patients will be questioned about AEs at each visit to the clinic.

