Study Drug administration ²¹				X	X	X	X		
Leakage Measure ²²				X	X	X	X		

1. Date of birth, gender, race, height (cm), weight (kg).
2. Medical History (including UC history) is to include the entire screening period, until just prior to the first dose of study drug with exception of AEs related to study procedures.
3. Blood pressure and heart rate at every visit (except visit 1b and 2a), body temperature, height and weight only at Visit 2b.
4. The following system organ classes will be reviewed for any relevant findings and appropriate physical examinations should be performed: general appearance, skin, musculoskeletal, eyes, ears, nose, throat, thyroid, cardiovascular, chest, abdomen, lymph nodes and neurological examination. Clinically significant findings will be reported as medical history prior to first dose of study drug and thereafter as an AE.
5. Haemoglobin, haematocrit, platelet count, RBC, WBC, platelets, neutrophil, eosinophil, basophil, lymphocyte, and monocytes count. Fibrinogen, APTT and PT (including INR) in non-fasting samples.
6. Albumin, alkaline phosphatase (ALP), alanine aminotransferase (ALT), aspartate aminotransferase (AST), amylase, blood urea nitrogen (BUN), calcium, chloride, creatine phosphokinase (CPK), creatinine, gamma glutamyl transferase (GGT), glucose, phosphorus, potassium, sodium, total bilirubin, total protein, uric acid, in non-fasting samples.
7. Total cholesterol and triglyceride, in non-fasting samples.
8. Blood, glucose, ketones, leucocytes, nitrite, protein, pH.
9. Stool culture of Clostridium difficile Toxin B, Shigella, Campylobacter, Yersinia and Salmonella, as well as ova and parasites.
10. Only for females of childbearing potential; Serum pregnancy test at screening visit 1a and then dip-stick tests at all other occasions.
11. Serum CRP and faecal calprotectin.
12. A 12 lead ECG will be done at screening visit 1a and visit 6. On visit 2b, ECG will be taken before study drug administration and 30 minutes after treatment.
13. A full colonoscopy will be required at visit 1b, and flexible sigmoidoscopy at primary endpoint, visit 6. Videos will be sent for central reading and biopsies collected for histopathological grading according the Nancy score and future biomedical research (if consented). 3 biopsies should be taken from each bowel segment investigated (see protocol section 7.7; separate instructions are provided).

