14. Patient will be prompted to fill in the e-diary on a daily basis. Patient should be instructed how to use the eDiary at visit 1a and if needed on all visits.
15. PGA will be assessed at visit 1b (if not eDiary data are available then at visit 2a) and at visit 6 and 7
16. IBDQ should be filled in before administration of study drug.
17. The patients will be questioned about AEs at each clinic visit. Only AEs related to study specific procedures at screening visit will be recorded at Visit 1a, 1b and 2b.
18. There will be questions regarding Extra Intestinal Manifestation disease/symptoms at visit 2b, visit 6 and visit 7.
19. All concomitant medication taken should be reported at each visit. UC treatment should be reported up to 3 years before screening visit. For UC treatment dose and start and stop date will be reported for the last treatment period.
20. Inclusion/exclusion criteria will be reviewed at several occasions during the screening period up to randomisation e.g when the results of the safety laboratory and stool culture analyses have been obtained. When central reading result has been obtained a telephone contact visit will be done to ensure patient is still willing to participate and that all inclusion and exclusion criteria still are fulfilled. Randomisation procedure will then commence and patient will be scheduled for the first treatment visit.
21. The study drug solution will be administered by the physician using a rectal enema. The exact time for start of the administration will be recorded in the eCRF.
22. Any leakage of study drug should be recorded in the eCRF.

Figure 1. Study Design

Clinical Study Protocol

CSUC-01/16

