5.2. Study Drug Administration

Cobitolimod and matching placebo will be provided to the study sites by InDex Pharmaceuticals AB or its representative. Cobitolimod is a solution of 0.62 mg/mL (31 mg) and 2.5 mg/mL (125 mg) and 5 mg/mL (250 mg) drug in 50 mL water for injection in single-use siliconised glass vials with rubber stopper and aluminium cap.

The study drug will be administered only to eligible patients under the supervision of the investigator or identified designee(s). Female patients must have a negative urine pregnancy test prior to receiving each dose of study drug.

The study drug will be administered via a rectal enema while patients are in a lying left-sided position. All patients and study personnel will be blinded to study drug assignment for the entire study.

The time for start of the administration will be recorded in the eCRF. After administration the patient will be asked to remain recumbent for 30 minutes and it is allowed to move over to a bed. Any leakage (weight) of study drug will be recorded in the eCRF. The study drug will be administered at visit 2b, 3, 4 and 5. The visit schedule allows for a +/- 3 day deviation from the planned date of visit, and is always calculated from the day of visit 2b. At least three days must pass between visits and thus between the administration of study drug.

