6.2. Visit 2a (Day -4 to-7) and 2b (Week 0) – Randomisation Visits

When the Central reading assessment is available and UC disease is qualifying for the study, the patient will be contacted by phone, Visit 2a, to ensure patient is willing to participate in

the study. If the patient is found to be eligible for study participation, the investigator will follow a central randomisation procedure and obtain a unique number (Patient Identification number) for the patient. If the patient fails to fulfil the inclusion/exclusion criteria, the patient can be re-screened at a later time point. If the re-screening will take place more than 1 month after the first screening visit all procedures need to be re-done, otherwise the Sponsor/CRO will confirm to site which screening procedures have to be repeated at re-screening in order to ensure that the patient fulfils the criteria for entering the study. If the re-screening is performed more than 1 month after the first screening, patient will receive a new Patient Identification number.

The patient must be scheduled for the Visit 2b/Week 0 visit within 10 days from the performed endoscopy (including the day of endoscopy and first treatment).

At the visit 2b; before study drug administration vital signs (HR, BP and temperature) and physical examination will be performed. Females of childbearing potential will take a dipstick urinary pregnancy test. An ECG will be taken before study drug administration and approximately 30 minutes after treatment, before leaving the clinic.

The patient will be asked to complete an IBDQ questionnaire and extra intestinal manifestations and defecation urgency assessment will be obtained. Non-fasting blood samples will be collected for haematology, blood chemistry including CRP (biomarker) and future biomedical research (if consented to). Urine sample will be collected for dipstick analysis (Blood, Glucose, Ketones, Leucocytes, Nitrite, Protein and pH) and if clinically significant microscopy and/or culture will be sent to central laboratory. Stool sample for faecal calprotectin (biomarker) will also be collected. Repeated training and instructions for the patient eDiary handling will be given. It is important to ensure the patient understands that eDiary data are necessary to evaluate the study. Information on concomitant medication will be collected. Any AEs related to study specific procedures, will be recorded.

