The patient will thereafter receive the study drug they were allocated to during the randomisation procedure. The study drug will be administered with a rectal enema. Following study drug administration the patient will be asked to remain recumbent for at least 30 minutes. Any leakage will be measured.

All obtained information will be reported in the eCRF.

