6.3. Visit 3 - (Week 1)

This visit should occur on Day 7 (\pm 3 days). Vital signs (BP and HR) and physical exam will be measured. Non-fasting blood samples will be collected for haematology, blood chemistry including CRP (biomarker) and future biomedical research (if consented to). Stool sample for faecal calprotectin (biomarker) will also be collected. A dipstick urine pregnancy test should be checked. Defecation urgency assessment will be obtained. Repeated instructions for the eDiary handling will be given if necessary. It is important to ensure the patient understands that eDiary data are necessary to evaluate the study. Changes in concomitant medication or new medications should be reported. The patient will be treated with cobitolimod/placebo with a rectal enema. Following drug administration the patient will be asked to remain recumbent for at least 30 minutes. Any leakage will be measured. Patient will be asked if any AE has occurred since last visit.

All obtained information will be reported in the eCRF.

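### The protocol gives conflicting rules for events after the first dose at Visit 2b: a visit-based limit to procedure-related adverse events, against a first-dose boundary elsewhere

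*Combined protocol and SAP*

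**What the plan says.** Three places describe AE recording at Visit 2b by visit.

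- Section 8 (Adverse Event), in a parenthesis on investigators' duty to record AEs, allows only events related to study procedures to be "recorded at Visit 1 and 2 while any other medical finding will be recorded as medical history".
- Table 1, footnote 17: "Only AEs related to study specific procedures at screening visit will be recorded at Visit 1a, 1b and 2b".
- Section 6.2, in the list of tasks for Visit 2b: "Any AEs related to study specific procedures, will be recorded".

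Section 5.2 identifies the dosing visits: "The study drug will be administered at visit 2b, 3, 4 and 5". Visit 2b is therefore the first exposure. Section 6.2 adds: "Following study drug administration the patient will be asked to remain recumbent for at least 30 minutes". It also schedules an ECG about half an hour after treatment.

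Other places set the boundary by dose. Table 1 footnote 2 runs medical history "until just prior to the first dose of study drug with exception of AEs related to study procedures". Section 7.13 also ends medical history at the first dose. Footnote 4 and section 7.16 make clinically significant examination findings AEs once the first dose has been given. Section 7.5 sends ECG abnormalities seen before the first dose to medical history and treats findings during the study as AEs. Section 8.1 counts as an AE anything new or worse since study drug was given, and section 8.6 wants every AE in the eCRF.

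**The concern.** The purpose of the limit is plain: before treatment starts, intercurrent findings belong to the patient's history, and only harm from study procedures needs an AE entry. The difficulty is that the limit is attached to visit numbers, and one of the named visits straddles the first dose. In the second part of that visit the patient has had study drug and is still under observation.

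A non-procedural reaction seen then (pain or malaise, for example) has two possible destinations depending on which passage the site reads. If it goes to medical history, it leaves the AE tables and becomes part of the patient's baseline. AE incidence is a safety endpoint (section 3.2.3), and safety is the primary objective of the data safety monitoring board's review (section 9.12). About 90 sites are planned, so a rule open to two readings may also be applied differently from site to site.

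**Working it through.** No formula or stated figure is involved. The check is to take one case, a non-procedural finding first seen in the clinic after the first dose at Visit 2b, and see where each passage sends it.

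1. **Does the limit reach the dosing visit?** Section 8 says only Visit 2, which has two parts: 2a (a phone call) and 2b. Footnote 17 settles it by naming 2b, and section 5.2 confirms dosing at 2b.
2. **Does either limiting sentence stop at the dose?** Both refer to procedures at the screening visit, but neither says that the limit ends once drug is given. Read literally, section 8 sends the case to medical history and footnote 17 leaves it out of the AE record.
3. **What does section 6.2 add?** Its only AE line for Visit 2b is the procedure-related one. The text after dosing covers recumbency and leakage. Sections 6.3 to 6.5, for Visits 3 to 5, each carry an unrestricted AE question: "Patient will be asked if any AE has occurred since last visit". Section 6.2 has no equivalent.
4. **What do the dose-based passages say?** Footnote 2 and section 7.13 close medical history at the first dose, so the case cannot be history. Footnote 4 and section 7.16 make it an AE if it is an examination finding, and section 7.5 does so if it is an ECG finding. Sections 8.1 and 8.6 make it a recordable AE whatever its type.
5. **Result.** The same finding is medical history or unrecorded under steps 1 to 3, and an AE under step 4. Both rules cannot stand.
6. **What else would pick it up that day?** Section 7.23 has vital signs taken before treatment on dosing days. After the first dose, the scheduled assessments are the leakage measure and the ECG. That ECG is the only one in the trial timed shortly after a dose. Visit 6 also has an ECG, but at Week 6, three weeks after the last planned dose at Week 3.
7. **Exposure under the conflicting wording.** With 43 patients in each of five arms, all 5 × 43 = 215 have their first administration at Visit 2b, which is 1 of 4 administrations. Of these, 4 × 43 = 172 receive active drug. In the three two-dose arms this is 1 of 2 active doses. Over the four active arms, the planned active doses number 43 × (2 + 2 + 2 + 4) = 430, so first doses are 172 / 430 = 40%. These are shares of administrations. They do not estimate events lost, because the documents give no rate of acute reactions and no rate of misfiling.

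**The case against.** The strongest reply is that the intent is clear and most of the text supports it. Section 7.3 and the opening of section 8 confine the limit to the screening period. The parenthesis sits inside a sentence requiring all AEs to be recorded, and the next sentence has patients questioned about AEs at clinic visits following study drug administration. Section 6.1 says that AEs from study procedures will be recorded at Visit 2b, which suggests that 2b appears in footnote 17 as the look-back point for harm from the colonoscopy and other screening procedures. The Visit 3 question, and the eCRF record of start and end, could recover a reaction missed on the day. Serious events are reportable within 24 hours under section 8.7 regardless.

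Much of this stands, and it limits what can be claimed. A reader might infer that the rules discard all first-dose reactions. The documents do not support that, since several passages require those events to be recorded. A reader might also infer that a changed ECG after the first dose would be lost; section 7.5 has a specific rule making it an AE. The position of the AE line before the dosing paragraph in section 6.2 should not be pressed either: the same section describes the post-treatment ECG before it describes dosing, so the narrative is not chronological.

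The reply does not remove the contradiction. The limit in section 8 is an exception to the duty to record all AEs, so that duty does not by itself override it. The questioning sentence does not say that the patient is asked again at Visit 2b after dosing. The Visit 3 question covers the time since the last visit, and a brief reaction during Visit 2b can be read as outside that window.

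**Conclusion.** The point holds as an internal contradiction between a visit-based and a dose-based boundary for AE recording at Visit 2b. A site that follows section 8 or footnote 17 as written could omit a non-procedural reaction after the first dose or file it as medical history, which would understate AE incidence. The wording covers the first administration in every arm. The number of events affected cannot be derived from the documents and may be small, because the dose-based passages and the Visit 3 question would bring some or most of them back. It would go too far to read the 40% share of active doses as a share of reactions lost.

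The conclusion assumes that sites work from the protocol text. Site training material or eCRF completion guidelines that already apply the first-dose boundary would remove the practical effect, but these are not part of the documents. The correction is still worth making, because it is cheap and concerns the first exposure to the study drug.

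**What to change.** Use one boundary throughout, the one the protocol already applies to medical history, examination and ECG findings.

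- In section 8 and Table 1 footnote 17, replace the list of visits with a time rule: until the start of the first administration, record procedure-related AEs only; from that moment at Visit 2b, record all AEs.
- In section 6.2, apply the same rule, and state that the patient is asked about AEs after dosing and before leaving the clinic, so that Visit 2b carries an unrestricted AE question as Visits 3 to 5 do.
- Confirm that the Visit 2b AE page in the eCRF accepts non-procedural events.

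The cost is a change of wording in three places, one question at a visit where the patient is already kept for at least 30 minutes, and possibly a small eCRF change. Design, sample size and planned analyses are unaffected.
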